Table 1B. Characteristics of AD/ADRD Population with current evidence of inappropriate prescribing in Health Plans Jan January 2020-January 2021 after prioritization of Medication Classes #	
Number of health plan members with AD/ADRD	130,682
Antipsychotics N, %	12,581, 9.6%
Sedative hypnotics N, %	5,122, 3.9%
Strong anticholinergics N, %	8,556, 6.5 %
Number of health plan members with AD/ADRD and evidence of inappropriate prescribing N, %	26,259, 20.1%

Members prioritized with Antipsychotics > sedative-hypnotics>strong anticholinergics; Total inappropriate percentage=20.1

R33 Implementation Phase Aims: The R33 Implementation Phase aims are:

Aim 1: To assess the impact of the patient/caregiver educational intervention on the primary outcome of cessation of inappropriate prescribing among AD/ADRD patients, employing a prospective, randomized trial design with three arms: (1) a combined patient/caregiver and provider educational intervention; (2) a provider only educational intervention; and (3) usual care. Secondary outcomes will include any dose reduction of inappropriate medications, prevalence of polypharmacy; rates of emergency room visits; rates of hospitalizations; rates of non-acute institutional stays (e.g., skilled nursing facilities); overall health care utilization (number of outpatient visits, days hospitalized, emergency department visits, and non-acute institutional days); and inpatient mortality.

Aim 2: To create: (1) a plan for disseminating study findings to stakeholders who might implement the intervention or make decisions about its future use; and (2) an implementation toolkit for health plans and health systems wishing to implement the intervention.

[figure not shown]
R33 Phase (Aim 1): D-PRESCRIBE-AD is a **prospective, randomized, “open-label” educational intervention trial**.

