9.2 SAMPLE SIZE DETERMINATION

Sample Size and Power. Our target sample size for the first trial is 14,442 patients, 4814 patients in each of the three study arms. The calculations below employ 80% power, overall Type I error rate of .05 with a Bonferroni correction for 3 pairwise comparisons of study arms (.05/3=.0167), and 2-sided hypothesis testing. Based on our prior analyses,^{26,27} we anticipate death or health plan disenrollment in 9.9% of sampled patients within 3 months of the intervention (receipt of the letter), with the remaining 90.1% contributing data in the 6-month interval of interest (days 91-270 post-intervention) – that is, we anticipate a per-arm sample size of $4814 \times .901 = 4337$.

For analyses of the primary outcome, absence of dispensing of targeted inappropriate prescription classes in days 91-270, we anticipate censoring in this interval for 13.5% of participants based on prior data. To make maximal use of observed data, we will use survival analysis to model time until an inappropriate prescription (a “failure”) in days 91-270. Detectable pairwise between-arm differences (e.g., between usual care and an intervention arm) are presented in Table 2 below for a range of possible percentages for “failure” = inappropriate prescribing of the targeted drug.

Table 2. Detectable pairwise between-arm differences in hazard of inappropriate prescription classes in days 91-270

Percent with inappropriate prescribing of targeted drug (“failure”), Study Arm 1	Detectable hazard ratio for inappropriate prescribing, Arm 2 versus Arm 1
40	.8860
50	.8979
60	.9067
70	.9136
75	.9165
80	.9192
85	.9216
90	.9239
95	.9260
99	.9267

For the range of “failure” percentages examined here, which reflect those seen in Martin et al,³ detectable hazard ratios range from 0.89 to 0.93. For example, if 75% of participants randomized to Arm 1 are observed to have a “failure” (prescription for a targeted inappropriate medication) by day 270, the detectable hazard ratio for an inappropriate prescription for Arm 2 versus Arm 1 is 0.9165, a

8.35% reduction in risk; the corresponding detectable “failure” probability for Arm 2 = 0.7193, a difference smaller – i.e., more precise – than that seen in Martin et al.³ Calculations for the secondary outcome of ≥50% reduction in dose are parallel.

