9.4 STATISTICAL ANALYSES

9.4.1 GENERAL APPROACH

In descriptive analyses, treatment arms will be compared regarding key patient characteristics, including age, gender, and renewal of inappropriate prescriptions in days 1-90, using percentages for categorical characteristics and means (standard deviations) or medians (interquartile range) for continuous characteristics, depending on the observed distributions. Analyses of study outcomes will employ two-sided hypothesis testing and an overall Type I error of 0.05, applying a Bonferroni correction to accommodate three pairwise comparisons of the three study arms. Covariates of *a priori* interest include patient age, gender, and renewal of inappropriate prescriptions in the blackout period. In addition, we will adjust for characteristics that are found to predict study outcomes, in order to increase precision for the comparison of study arms,²⁸ as well as for characteristics found to be related to censoring or other missing data, in order to reduce possible nonresponse bias.²⁹ All analyses will be intention-to-treat. Sex as a biological variable will be factored into all analyses.

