9.4.2 ANALYSIS OF THE PRIMARY ENDPOINT(S)

PRIMARY OUTCOME

Statistical Analysis of Primary Outcome:

1. The primary outcome will be defined as absence of any dispensing of the targeted inappropriate prescription class from day 91 to day 270 following the day of mailing. Educational interventions will be targeted towards one specific drug class so participants who switch within one class (e.g. clonazepam to lorazepam) will not be considered as having met primary outcome. **The intervention will only target one potentially inappropriate medication class for patients who are on more than one class of potentially inappropriate medication.**
2. **Timing of Ascertainment:** The timing of ascertainment is over a 6-month period beginning 3 months after mailing/intervention – i.e., we will assess evidence of a dispensing in days 91 through 270 after the date of mailing.
3. **Method of Aggregation: Hazard ratio.** The data on primary outcome will be measured as the relative hazard of time to dispensing of any new incident inappropriate prescription of

their initial drug class in the intervention vs control group. The index date for the survival analysis will be Day 91 for the trial. We chose the hazard ratio as method of aggregation as this allows the statistical analysis to account for censoring due to death or disenrollment.

4. Any prescriptions dispensed during the **blackout period** will not be counted towards measurement of the primary outcome but may affect subsequent dispensing. In covariate-adjusted survival analyses, we will adjust for whether any prescription for the same inappropriate medication class was dispensed during the blackout period and the duration of such dispensing because dispensing during the blackout period is an important factor which may affect the primary outcome. A blackout period was needed to allow time for the mailing and receipt of the intervention after randomization, and the opportunity to set up the appointment with or contact their provider to discuss the use of the potentially inappropriate medication. Alternatively, we may also consider stratification of survival analyses by prescriptions dispensed during the blackout period.

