For the primary outcome (i.e., any post-intervention discontinuation of inappropriate prescribing during the 6-month period beginning 3 months after the mailing), as a first step, we will calculate crude arm-specific percentages, as well as Kaplan-Meier curves and log-rank testing. Covariate-adjusted comparisons of arms will be estimated using Cox proportional hazards modeling. Comparing active intervention arms to usual care, we hypothesize a hazard ratio of less than 1, indicating lower risk of an inappropriate prescription in days 91-270 in the active intervention arms. The index date for the survival analysis will be day 91. We chose the hazard ratio as method of aggregation as this allows the statistical analysis to account for censoring due to death or disenrollment. To account for mortality, anticipated to be approximately 6%, we also will conduct competing risk analyses³⁰ as well as cause-specific hazards modeling.³¹

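### The pooled primary analysis names neither its deciding test nor a closed covariate list, and omits target drug class and health plan; stratifying by both costs no power.

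*Combined protocol and SAP*

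**What the plan says.** Section 9.4.2 starts the primary analysis with a descriptive and testing step: "we will calculate crude arm-specific percentages, as well as Kaplan-Meier curves and log-rank testing". No strata are given for the test. It continues: "Covariate-adjusted comparisons of arms will be estimated using Cox proportional hazards modeling". The hazard ratio is fixed as the summary measure, but the section does not say whether the log-rank test or the Cox model decides the primary result.

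For the Cox model, section 9.4.1 says that covariates of a priori "interest include patient age, gender, and renewal of inappropriate prescriptions in the blackout period". Section 9.4.2 (item 4) adds the duration of blackout dispensing. Two open rules follow in 9.4.1. One is stated as "we will adjust for characteristics that are found to predict study outcomes, in order to increase precision for the comparison of study arms"; the other admits characteristics related to censoring or missing data. Neither has a candidate list, a selection criterion or a time at which it is applied.

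The only stratification raised for the primary survival analysis is optional: "Alternatively, we may also consider stratification of survival analyses by prescriptions dispensed during the blackout period".

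Target class is settled by a hierarchy before mailing (6.1.2; Table 1B in 4.1: "Members prioritized with Antipsychotics > sedative-hypnotics>strong anticholinergics"). It determines which materials are sent and which dispensings count as failure. It appears in separate by-class analyses (9.4.7, 9.4.9), but not in the pooled comparison. Health plan is not named as a covariate or stratum anywhere.

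**The concern.** Several pooled analyses fit this text: an unstratified log-rank test, a Cox model with or without class, and a survival analysis stratified by blackout dispensing. They can disagree on significance in the same data. The reader of trial 1 could not tell from the plan which one was the primary result.

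Class is the obvious baseline factor to name. Dispensing of an antipsychotic, a sedative-hypnotic and a strong anticholinergic may well persist at different rates. If so, pooling without strata pulls the hazard ratio towards 1, away from the within-class value, and the log-rank test loses power.

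The named covariate closest to the outcome has a different problem. Section 9.4.2 says that the blackout allows for receipt of the mailing and "the opportunity to set up the appointment with or contact their provider to discuss the use of the potentially inappropriate medication". Renewal in days 1 to 90 can therefore already carry some of the intervention's effect, and conditioning on it can remove that part.

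**Working it through.** **Plan's own figure.** Section 9.2 tabulates "Detectable pairwise between-arm differences in hazard of inappropriate prescription classes in days 91-270". Inputs from 9.2: 4,814 x 0.901 = 4,337 per arm; 13.5% censoring; 75% failure in Arm 1; hazard ratio 0.9165; two-sided alpha 0.05/3.

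- Arm 2 failure: 1 - 0.25^0.9165 = 0.7193, as printed.
- Events: 4,337 x (0.75 + 0.7193) x 0.865 = 5,512.
- Power (Schoenfeld): Phi(sqrt(5,512)/2 x 0.0872 - 2.394) = Phi(0.843) = 80.0%. The plan's figure is reproduced.

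**Assumptions for the check.** Class shares come from Table 1B: 12,581, 5,122 and 8,556 of 26,259, or 47.9%, 19.5% and 32.6%. This is the feasibility cohort, not the randomised sample. The plan split of 11,250 to 3,192 is inferred from the July 2022 amendment entry. The documents give no class-specific failure rates, so a range is assumed, with a common within-class hazard ratio of 0.9165.

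**Log-rank power.** 9,600 simulated trials per row, 4,337 per arm, exponential times, 13.5% contributing no event, Monte Carlo standard error about 0.4 points:

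| Assumed control failure %, antipsychotic / sedative-hypnotic / anticholinergic | Unstratified | Stratified by class and plan | Gain (points) | Pooled hazard ratio |
|---|---|---|---|---|
| 75/75/75 | 80.0% | 80.1% | 0.1 | 0.916 |
| 78/75/72 | 80.1% | 80.5% | 0.4 | 0.917 |
| 80/75/68 | 78.8% | 79.7% | 0.9 | 0.918 |
| 85/75/60 | 74.2% | 79.0% | 4.8 | 0.921 |
| 90/70/50 | 65.2% | 78.6% | 13.4 | 0.927 |

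The two tests reach different conclusions on significance in 0.7% to 17.6% of trials across these rows.

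**Hand check of the last row.** Control failure is 0.479 x 0.90 + 0.195 x 0.70 + 0.326 x 0.50 = 0.731. Applying 0.9165 within each class gives 0.705 in the intervention arm. Events: 4,337 x (0.731 + 0.705) x 0.865, about 5,385.
- At the diluted ratio 0.927: Phi(36.69 x 0.0758 - 2.394) = Phi(0.387) = 65%.
- At 0.9165: Phi(36.69 x 0.0872 - 2.394) = Phi(0.805) = 79%.

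Both agree with the simulation.

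**Cost of six strata when neither factor matters.** In a separate simulation with more events per trial (6,034), the log-rank information fell from 1,507.2 to 1,505.5, or 0.11%. That is about 6 of 5,512 events. Power was 83.5% both ways. In the same runs plan added 0 to 1 point, and class supplied nearly all of the gain.

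**Blackout adjustment.** One assumed scenario: class failure 85/75/60%, renewal 90/80/65%, renewal hazard ratio 5, baseline supply correlated 0.6 with renewal, 2,400 trials each.

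| Share of effect acting through blackout renewal | Cox with renewal and class | Cox with baseline supply, stratified by class and plan |
|---|---|---|
| None | 94.4% | 87.3% |
| A quarter | 73.7% | 83.8% |
| A half | 34.9% | 77.4% |

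Duration of blackout dispensing is not modelled, so these figures are illustrative only.

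**The case against.** The strongest reply is that the Cox model probably corrects itself. Section 9.4.1 commits to adjusting for predictors of outcome and does not limit which, and the named covariates are introduced as a non-exhaustive list. If class is a candidate, a p<.05 rule selects it in at least 99.7% of trials in the three most unequal rows above, and the Cox loss is about 0. This stands. Only if class were not a candidate would the Cox model lose power: renewal alone against renewal plus class differs by -0.3 to 1.3 points at 80/75/68, 1.1 to 4.8 at 85/75/60 and 4.6 to 11.2 at 90/70/50. The text does not require that reading.

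It is also fair that the log-rank test, read literally, is fixed as unstratified and is called a first step. What is open is which analysis decides, and what enters the Cox model. The larger gains need wide class differences that no document reports; at 78/75/72 and 80/75/68 the gain is under 1 point.

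A reader might infer inflated Type I error. The documents do not support that. Each single test keeps its level. With the null true, rejecting if any of four stratification choices was significant gave 1.5% to 2.7% against a nominal 1.67%, with a Monte Carlo standard error of about 0.3 to 0.4 points. Selection made without regard to arm need not inflate error at all.

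A reader might also infer that covariates will be picked with the arm comparison in view, or that the pooled result settles what trial 2 drops. Section 9.4.1 states no timing. Section 4.1 says only that trial 2 may be adapted on trial 1 experience, and the by-class analyses bear more directly on limiting classes. The pooled result may inform those choices; it does not decide them.

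**Conclusion.** The point holds as a gap in prespecification with a better analysis available. The plan does not identify the deciding test, leaves the Cox covariates open, and omits two factors known for every patient before mailing.

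Stratifying by class and plan loses no power at equal class rates. It gains the first-step log-rank test about 0 to 13 points over the assumed range, with nearly all of that from class. No gain is established for the Cox model if the selection rule would bring class in. These sizes rest on assumed class failure rates, the feasibility class mix, an inferred plan split and one common within-class hazard ratio.

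Conditioning on blackout dispensing is a separate weakness, supported by the plan's own account of what the blackout is for. How much it matters depends on how far the mailing changes renewal in days 1 to 90, which the documents do not say. This is a change that should be made; it does not show that the trial is underpowered or its error rate compromised.

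**What to change.** Before outcomes are analysed, amend 9.4.1 and 9.4.2 as follows.

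1. Name one primary analysis: a Cox model stratified by target drug class and health plan, with a fixed list of pre-randomisation covariates (for example age, sex, comorbidity score and pre-mailing days' supply of the target class). Give the log-rank test the same strata and state that it is supportive. Report the hazard ratio as a within-stratum one, since it differs slightly from the pooled ratio when classes differ.
2. Move outcome-driven and censoring-driven covariate selection to sensitivity analyses. Do the same with adjustment for, or stratification by, blackout dispensing.

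The strata in the first change are free: the wording changes, no patients are added, both factors are already held, and no power is lost. Pre-randomisation dispensing is already needed for the dose-reduction outcome in 9.4.3.

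The second change is not free in every case. In the scenario above it gives up about 7 points (94.4% to 87.3%) if the mailing leaves blackout renewal unchanged, and gains about 10 (73.7% to 83.8%) if a quarter of the effect acts through renewal. The reason to accept that trade is that the primary estimate then cannot have part of the effect adjusted away.

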9.4.2 ANALYSIS OF THE PRIMARY ENDPOINT(S)

PRIMARY OUTCOME

Statistical Analysis of Primary Outcome:

1. The primary outcome will be defined as absence of any dispensing of the targeted inappropriate prescription class from day 91 to day 270 following the day of mailing. Educational interventions will be targeted towards one specific drug class so participants who switch within one class (e.g. clonazepam to lorazepam) will not be considered as having met primary outcome. **The intervention will only target one potentially inappropriate medication class for patients who are on more than one class of potentially inappropriate medication.**
2. **Timing of Ascertainment:** The timing of ascertainment is over a 6-month period beginning 3 months after mailing/intervention – i.e., we will assess evidence of a dispensing in days 91 through 270 after the date of mailing.
3. **Method of Aggregation: Hazard ratio.** The data on primary outcome will be measured as the relative hazard of time to dispensing of any new incident inappropriate prescription of

their initial drug class in the intervention vs control group. The index date for the survival analysis will be Day 91 for the trial. We chose the hazard ratio as method of aggregation as this allows the statistical analysis to account for censoring due to death or disenrollment.

4. Any prescriptions dispensed during the **blackout period** will not be counted towards measurement of the primary outcome but may affect subsequent dispensing. In covariate-adjusted survival analyses, we will adjust for whether any prescription for the same inappropriate medication class was dispensed during the blackout period and the duration of such dispensing because dispensing during the blackout period is an important factor which may affect the primary outcome. A blackout period was needed to allow time for the mailing and receipt of the intervention after randomization, and the opportunity to set up the appointment with or contact their provider to discuss the use of the potentially inappropriate medication. Alternatively, we may also consider stratification of survival analyses by prescriptions dispensed during the blackout period.

For the primary outcome (i.e., any post-intervention discontinuation of inappropriate prescribing during the 6-month period beginning 3 months after the mailing), as a first step, we will calculate crude arm-specific percentages, as well as Kaplan-Meier curves and log-rank testing. Covariate-adjusted comparisons of arms will be estimated using Cox proportional hazards modeling. Comparing active intervention arms to usual care, we hypothesize a hazard ratio of less than 1, indicating lower risk of an inappropriate prescription in days 91-270 in the active intervention arms. The index date for the survival analysis will be day 91. We chose the hazard ratio as method of aggregation as this allows the statistical analysis to account for censoring due to death or disenrollment. To account for mortality, anticipated to be approximately 6%, we also will conduct competing risk analyses³⁰ as well as cause-specific hazards modeling.³¹

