Objectives*:	
Primary Objective: To assess the impact of the patient/caregiver educational intervention on inappropriate prescribing to AD/ADRD patients.
 
Secondary Objectives: To create: (1) a plan for disseminating study findings to stakeholders who might implement the intervention or make decisions about its future use; and (2) an implementation toolkit for health plans and health systems wishing to implement the intervention.

Endpoints/Outcomes:	
Primary Endpoint: We will evaluate the effect of educational interventions designed to stimulate patient/caregiver-provider communication about medication safety (versus usual care) on the primary outcome. The primary outcome will be defined as absence of any dispensing of the targeted medication from day 91 to day 270 during the 9 months following receipt of intervention.
 
Secondary Endpoints: Secondary outcomes are listed below. These will also be assessed specific to the 6-month observation period (days 91-270 following mailing/intervention) based on health plan claims data including:
 
 a) Any dose reduction (defined as $\geq 50\%$ reduction in dose of the targeted medication), assessed at the participant level using health claims data (outpatient dispensing). b) Percentage of patients with polypharmacy. (defined as >5 active prescriptions for different oral agents) c) Decline in the rates of: emergency room visits; rates of hospitalizations; rates of non-acute institutional stays (e.g., skilled nursing facilities); and overall health care utilization (number of outpatient visits, days hospitalized, emergency department visits, and non- acute institutional days). d) In-hospital all-cause mortality. (We can only study in-hospital all-cause mortality due to a delay in receipt of comprehensive death data.) We will use administrative claims data to identify encounters of interest (ED visits, hospitalizations, non-acute institutional stays, outpatient visits) and only assess oral formulations for medications. e) Among study subjects who discontinue the targeted medication, we will determine if another agent within the targeted class has been dispensed over the period of observation (day 91-270).

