2 INTRODUCTION

2.1 STUDY RATIONALE

Potentially inappropriate prescribing includes the use of medications that may no longer be necessary or that may increase the risk of harm. Inappropriate prescribing can lead to adverse drug events, falls, worsening cognitive impairment, and emergency hospitalizations. Inappropriate prescribing is a “morbidity multiplier,” increasing overall symptom burden, and adversely affecting health-related quality of life and function. Inappropriate prescribing of certain drug categories, such as sedative-hypnotics, antipsychotics, and strong anticholinergic agents, poses particular risks for older adults and may be more prevalent among those with Alzheimer’s disease and Alzheimer’s disease-related dementias (AD/ADRD) due to a higher prevalence of multimorbidity and associated polypharmacy.²

Enhancing patient/caregiver communication with the healthcare provider about medications may help reduce inappropriate prescribing to persons with AD/ADRD. The overarching goal of our proposal is to develop, implement, and evaluate the effect of a patient/caregiver-centered, multifaceted educational intervention on inappropriate prescribing in patients with AD/ADRD. The Developing a PRogram to Educate and Sensitize Caregivers to Reduce the Inappropriate Prescription Burden in Elderly with Alzheimer’s Disease Study (D-PRESCRIBE-AD) will be a large, randomized, pragmatic trial to test a health plan-based intervention leveraging the NIH Collaboratory’s Distributed Research Network, which uses the Food and Drug Administration (FDA) Sentinel Initiative infrastructure. In this study, we will enroll community dwelling AD/ADRD patients (based on a diagnosis of AD/ADRD or use of a medication for AD), who have evidence of inappropriate prescribing. We will evaluate the effect of educational interventions designed to stimulate patient/caregiver-provider communication about medication safety (versus usual care) on the cessation of inappropriate prescribing, **the primary outcome** of this study. The educational intervention will be an adaptation of an intervention proven effective in reducing the use of inappropriate medications in older adults,³ modified for the AD/ADRD population and their caregivers.

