Measurement of Dose Reduction. We will consider dose reduction for each selected drug as being a $\geq 50\%$ decrease in the mean daily dose comparing the 6 months immediately prior to the randomization with the 6-month study window period. (day 91-day 270). We will measure average daily dose using dates of prescription dispensing, duration of prescription dispensing and strength of the prescription. We will measure the dose reduction as a dichotomous variable defined as the proportion of patients who achieved a more than 50% dose reduction in the daily dose during the study window period (day 91 to day 270) compared to the 6-month period prior to randomization. Measurement of dose reduction over 6 month follow-up requires participants to complete follow-up through end of observation period (day 270). Censored participants – that is, those who have less than 6 months in days 91-270 – will be excluded for the analysis of dose reduction. Analyses will adjust for correlates of missing data. Analyses for post-intervention polypharmacy prevalence will be analogous. We will identify participants with evidence of dispensings of ≥ 5 oral medications over the respective 6-month periods [during the study window period (day 91 to day 270) compared to the 6-month period prior to mailing]. AD medications and the three potentially inappropriate medication classes will contribute to measure of polypharmacy. Injectables and topical or ocular medications will not be counted as evidence of polypharmacy.

A combination drug will be considered a single medication for the purpose of this analysis. Additional analyses will examine within-patient change in number of inappropriate medications, where the maximum possible decrease equals the pre-intervention number of inappropriate medications. We will accommodate this between-patient heterogeneity as follows: within-patient changes will be ranked separately by pre-intervention number of inappropriate medications, ranks will be transformed using normal scores to obtain comparable distributions across these strata, and treatment arms will be compared regarding transformed ranks³⁴ using analysis of covariance. In analyses of other secondary outcomes, count outcomes such as per-patient number of emergency department (ED) visits will be analyzed using Poisson or negative binomial regression, accounting for “excess” zeros if warranted based on observed distributions.³⁵

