Among study subjects who discontinue the targeted medication, we will determine if another agent within the targeted class has been dispensed over the period of observation (day 91-270). For sedative/hypnotics: dispensing of a new generic agent within the class of sedative/hypnotics. For antipsychotics: dispensing of a new generic agent within the class of antipsychotics. Analyses will be analogous to those for dose reduction.

Mortality will be analyzed using survival analyses, including Kaplan-Meier curves, log-rank testing, and Cox proportional hazards (PH) modeling, accounting for censoring due to disenrollment

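### The primary outcome counts a move from the targeted class to another listed class as success, and no planned analysis identifies those patients

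*Combined protocol and SAP*

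**What the plan says.** **What is being targeted.** Section 4.1 takes inappropriate prescribing to cover sedative-hypnotics, antipsychotics and strong anticholinergics. Section 2.1 says that inappropriate prescribing of such categories "poses particular risks for older adults and may be more prevalent among those with Alzheimer’s disease". Sections 4.1 (including Aim 1) and 9.4.2 describe the primary outcome as stopping inappropriate prescribing, without limiting that phrase to one class.

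**How the primary outcome is scored.** In 9.4.2 the definition is class-specific: "The primary outcome will be defined as absence of any dispensing of the targeted inappropriate prescription class from day 91 to day 270". The event in the survival model is a dispensing of "their initial drug class in the intervention vs control group". For patients on several classes, "The intervention will only target one potentially inappropriate medication class for patients who are on more than one class of potentially inappropriate medication". On switching, the section says only that "participants who switch within one class (e.g. clonazepam to lorazepam) will not be considered as having met primary outcome".

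**How substitution is measured.** Item e) of the synopsis says of patients who stop the targeted drug that "we will determine if another agent within the targeted class has been dispensed over the period of observation (day 91-270"). Section 9.4.3 repeats this and adds one line for sedative-hypnotics and one for antipsychotics ("For antipsychotics: dispensing of a new generic agent within the class of antipsychotics").

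**The nearest broader measure.** Also in 9.4.3: "Additional analyses will examine within-patient change in number of inappropriate medications". Changes are ranked within strata of the pre-intervention number, converted to normal scores and compared by analysis of covariance.

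**The concern.** The endpoint is narrower than the claim it serves. A patient moved from the targeted class to another listed class still has inappropriate prescribing by the protocol's own description, yet counts as a success. The plan closes this route inside the class and leaves it open between classes.

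The trial 1 result may shape trial 2 and feeds the dissemination toolkit (4.1). Little else in the plan would show a shift between classes: safety analyses are marked not applicable (9.4.4), adverse events are not ascertained (8.3), and the by-class analyses (9.4.7, 9.4.9) repeat the same class-specific endpoint.

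**Working it through.** **Step 1. Score typical patients under each planned measure.** Take patients targeted for an antipsychotic. The last column assumes that the change-in-number analysis counts all three classes. Ranking by pre-intervention number implies this, but the text does not say it.

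| Baseline | Days 91-270 | Primary | Outcome e) | Change in number |
|---|---|---|---|---|
| Antipsychotic | Same antipsychotic | Failure | No | 0 |
| Antipsychotic | No listed class | Success | No | -1 |
| Antipsychotic | Different antipsychotic | Failure | Yes | 0 |
| Antipsychotic | Newly started sedative-hypnotic only | **Success** | **No** | **0** |
| Antipsychotic and sedative-hypnotic | Sedative-hypnotic only | Success | No | -1 |

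- A primary success has no dispensing in the targeted class in days 91-270, so it cannot have a within-class substitute in that window. Outcome e) is silent on every primary success.
- The change-in-number score gives the switched patient 0, the same as a patient who changed nothing. It does not credit the swap, but it does not identify the switcher or give the share of successes that were switches.

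**Step 2. Reproduce the plan's detectable effect (9.2).** Inputs: 4,814 x 0.901 = 4,337 per arm; 13.5% censoring; alpha 0.05/3, two-sided; 80% power; 75% failure in Arm 1; hazard ratio (HR) 0.9165.

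- Arm 2 failure: 1 - (1 - 0.75)^0.9165 = 0.7193, as printed.
- Events available: 4,337 x (0.75 + 0.7193) x 0.865 = 5,512.
- Events required (Schoenfeld): 4 x (z for alpha + z for power)^2 / (ln 0.9165)^2 = 5,509. The printed HR is reproduced.
- Difference: 0.75 - 0.7193 = 0.0307, or 3.07 points. On the risk scale that is 0.0307 x 4,337 = 133 patients per arm. After 13.5% censoring, the expected difference in observed events is 133 x 0.865 = about 115.

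**Step 3. Pure transfer, as an illustration.** Suppose no one in the intervention arm truly leaves all listed classes, but a net excess x over usual care moves from the targeted class to another. Then p2 = 0.75 - x, HR = ln(1 - p2) / ln(0.25), and events = 4,337 x (0.75 + p2) x 0.865.

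| Net excess x | Patients per arm | Primary HR | Probability of significance |
|---|---|---|---|
| 1 point | 43 | 0.9717 | 9% |
| 2 points | 87 | 0.9445 | 40% |
| 3.07 points | 133 | 0.9164 | 80% |
| 4 points | 173 | 0.8929 | 96% |
| 5 points | 217 | 0.8685 | 99.7% |

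The documents give no value for x. The table shows what would be needed, not what is expected.

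**Step 4. Patients already on more than one class (Tables 1A and 1B).** The hierarchy moved 6,617 - 5,122 = 1,495 sedative-hypnotic users and 11,228 - 8,556 = 2,672 strong-anticholinergic users to a higher class. The number on more than one class lies between 2,672 (full overlap of these groups) and 1,495 + 2,672 = 4,167 (none). That is 10.2% to 15.9% of 26,259. The two captions name different years, but the totals agree, so I read them as one cohort. These patients can stop the targeted class and continue another without any switch.

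**The case against.** The class-specific outcome is a deliberate choice. Section 4.1 says that one class will be evaluated, with a hierarchy set in consultation with the Advisory panel, and it is coherent to measure the class named in the letter. That stands, and the primary outcome should not change.

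A reader might infer three stronger things that the documents do not support:

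- **That substitution is looked for only within class.** The change-in-number analysis probably spans all three classes, and all three count toward polypharmacy. Emergency visits, hospitalizations and in-hospital mortality are also compared by arm. These are real secondary checks, but they are net or indirect and none isolates a switch.
- **That strong anticholinergics have no substitution rule.** The general sentence in 9.4.3 covers any targeted class. Only the class-specific line is missing.
- **That a known part of any benefit would be transfer.** No switching rate is given. Converting an assumed share of switches into a net fall in exposure to any listed class would also ignore the roughly 10-16% already on more than one class.

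Sections 2.2 and 4.1 also use the word inappropriate to mean a need to weigh risks against benefits, so a move between classes is not shown to be harmful in itself. That limits the point to what a positive result can be said to mean.

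**Conclusion.** The point holds in limited form. The primary outcome credits a move to another listed class, the named substitution outcome cannot see it among primary successes, and the change-in-number analysis does not identify these patients. A positive primary result would therefore show reduced dispensing of the targeted class. It would not show whether inappropriate prescribing as the protocol describes it had fallen or had partly moved.

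Whether this is material is unknown. About 3 points of net excess switching would be needed to mimic the detectable effect, assuming 75% failure in usual care, the plan's censoring, proportional hazards and no true reduction. Smaller excesses would inflate a real effect rather than create one. This is an inexpensive improvement worth making before outcomes by arm are examined, not a defect that invalidates the design.

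**What to change.** Keep the class-specific primary outcome.

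1. **9.4.3, item e).** Add any dispensing in days 91-270 of a non-targeted listed class that was not dispensed in a stated baseline look-back. The 6 months before randomization, already used for dose, would serve. Report it by arm and by targeted class, among all participants entering day 91 and separately among primary successes. The first is a randomized comparison apart from losses before day 91. The second describes the successes and is conditional on a post-randomization outcome.
2. **9.4.2.** Add a sensitivity analysis of the primary outcome in which such a new dispensing counts as failure. State that continued use of another class present at baseline is not a switch, and report it separately.
3. **9.4.3.** For consistency, add a strong-anticholinergic line beside the two existing class-specific lines.
4. Report these results together with the trial 1 results.

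The cost is SAP wording and a few lines in the distributed program. The dispensing claims are already used for eligibility, polypharmacy and the medication count. The downside is one more secondary outcome and a sensitivity result that may be less favourable than the primary.
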